3.1.3 Analysis phase windows

For the purpose of the statistical analysis, the assessments will also be assigned to the analysis phase in which they are collected as reported in [Table](#). In case of partially missing date, the imputed date will be used to assign the analysis phase.

Table 4 Analysis phase

Analysis phase	Phase window for analysis (Days)
Pre-treatment	Before first dose of study treatment (<= 1 ^(a))
On-treatment	From Day 1 ^(b) /Visit 3 up to and included 28 days after the last dose of study treatment
Follow-up	More than 28 days after the last dose of study treatment

^(a) Includes measurements collected prior day 1 or at day 1 prior to the first dose of study treatment. If measurement is done on day 1 but time of collection is missing and per CSP parameter should be collected before first dose of study, analysis phase is “Pre-treatment”.

^(b) Includes measurements collected at day 1, at the time of study treatment intake and after.

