Disclosure Statement: This is a parallel-group, treatment study with 6 intervention groups (including the legacy **CCI** mg dose group and matched placebo) that is participant- and investigator-blinded.

Number of Participants: Approximately 400 participants will be randomly assigned to a study intervention, with an anticipated 369 participants being randomized to receive active study intervention (123 participants in each of the 2 MEDI6570 groups), and 123 participants being randomized across the 3 placebo groups (ie, including participants already randomized to the legacy dose/volume-matched placebo group for the **CCI** mg dose). It is estimated that approximately 360 evaluable participants (111 evaluable participants in each of the 2 MEDI6570 groups [**CCI** and **CCI** mg], plus 27 evaluable participants in the legacy **CCI** mg MEDI6570 group, plus 111 participants across the 3 placebo groups) will complete the study. Evaluable participants are defined as those with an evaluable CTA at baseline and follow-up (Day 253; Visit 13).

Intervention Groups and Duration: The study intervention is MEDI6570, a human Immunoglobulin G1 lambda (IgG1 λ) triple mutation antibody that binds to **CCI** **CCI** Going forward from Amendment 2, the study will include 4 intervention groups: **CCI** and **CCI** mg MEDI6570, and 2

injection/volume-matched placebo groups, while the participants previously randomized to [REDACTED] mg MEDI6570 or its injection/volume-matched placebo will continue their assigned treatment to the end of the study. Participants will be enrolled in the study for up to approximately 12 months, comprising an optional pre-screening period of up to 42 days (6 weeks), a screening and pre-randomization period of up to 42 days (6 weeks), an intervention period of 225 days (31 to 32 weeks), and a follow-up period of 100 days (approximately 14 weeks). Doses of MEDI6570 or placebo will be administered in the clinic SC Q4W for 32 weeks (9 doses in total).

Data Monitoring Committee: Yes

Statistical Methods:

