Table 4 Schedule of Activities: Intervention Period

Procedure	Visit:	3	4	5	6	7	8	9	10	11	12	Notes	Details in CSP section or appendix
	Day (± 7): ^a	1	10 ^a	29	57	85	113	141	169	197	225		
Observational period		X		X								Participant must be in clinic for 2 hours after dosing.	Section 8.2.5.2
Assessment of AEs/SAEs		X	X	X	X	X	X	X	X	X	X		Section 8.3
Concomitant medications		X	X	X	X	X	X	X	X	X	X		Section 6.5
Assess for injection site reactions		X		X	X	X	X	X	X	X	X		Section 8.2.5.3

^a The visit window is ± 7 days for dosing visits and ± 3 days for non-dosing visits (ie, Day 10 [Visit 4]). If a participant is dosed outside of the visit window, he or she should return to the initial planned schedule for subsequent visits.

AE, adverse event; CSP, Clinical Study Protocol; CV, cardiovascular; ECG, electrocardiogram; HIV, human immunodeficiency virus; CCI [REDACTED]

NT-proBNP, N-terminal prohormone brain natriuretic peptide; PK, pharmacokinetic(s); SAE serious adverse event; CCI [REDACTED]

Table 5 Schedule of Activities: Follow-up Period

Procedure	Visit:	13	14	Notes	Details in CSP section or appendix
	Day:	253 (- 4 to + 11 days)	325 (± 7 days)		
End of study visit			X		Section 4.3
Full physical examination			X		Section 8.2.1
Weight			X		Section 8.2.1
Vital signs		X	X	Whenever vital signs and blood draws are scheduled for the same nominal time, the blood draws should occur last.	Section 8.2.2

Table 5 Schedule of Activities: Follow-up Period

Procedure	Visit:	13	14	Notes	Details in CSP section or appendix
	Day:	253 (- 4 to + 11 days)	325 (± 7 days)		
ECGs		X	X		Section 8.2.3
Assessment of AEs/SAEs		X	X		Section 8.3
Concomitant medications		X	X		Section 6.5
Collect blood for:					
Clinical safety (clinical chemistry and hematology)		X	X		Section 8.2.4
PK		X	X		Section 8.5.1
CCI		X	X	Sample collected on Day 325 will be stored.	Section 8.6.1
CCI NT-proBNP		X			Section 8.6.1
Circulating biomarkers of inflammation CV disease		X			Section 8.6.1
Immunogenicity		X	X		Section 8.5.2
Creatinine for calculating eGFR		X		should occur within 30 days before the CTA; either local laboratory or point of care testing can be used.	Section 8.2.4
Collect urine for:					
Future use (optional)		X		Sample will be collected and stored.	Section 8.6.2
Echocardiogram		X			Section 8.1.1 and 8.1.2 (including instructions for repeating uninterpretable

Table 5 Schedule of Activities: Follow-up Period

Procedure	Visit:	13	14	Notes	Details in CSP section or appendix

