4.2.10.8 Laboratory evaluation

Laboratory evaluations are described in section 3.3.5.2. Baseline and post-baseline definitions are detailed in section 3.1.2. All tables and listings for laboratory data will be based on the as-treated population and presented for each treatment group in IDMC reports and at final analysis.

Laboratory test results for haematology, coagulation and clinical chemistry quantitative parameters will be summarized, with their units of measure, with n, mean, SD, median, minimum, and maximum at each visit and for change from baseline.

Shifts from baseline to maximum and minimum value during the on-treatment phase will be presented for haematology and clinical chemistry parameters.

All individual laboratory data for haematology, coagulation and clinical chemistry will be also presented in a listing in that order.

In addition to the tables above, as described in the study protocol, also the following will be presented:

- Plots for the maximum on-treatment ALT/maximum on-treatment AST by maximum total bilirubin, expressed as multiples of ULN for assessing Hy's law criteria,
- List of key subject information for subjects with potential Hy's law combined ALT or AST, and bilirubin, and
- Proportion of subjects with elevated liver test based on measured laboratory values

In the 3 tables and figures listed above all measurements including unscheduled visits will be taken into account.

Elevated liver tests are defined as elevations from baseline up to the end of the study as follows:

ALT elevations

- ALT > 3xUpper Limit of Normal (ULN)
- ALT > 5xULN
- ALT > 10xULN
- ALT > 20xULN

AST elevations

- AST > 3xULN
- AST > 5xULN
- AST > 10xULN
- AST > 20xULN

AST or ALT elevations

- ALT or AST > 3xULN
- ALT or AST > 5xULN
- ALT or AST > 10xULN
- ALT or AST > 20xULN

Total bilirubin (BILI) elevations

- BILI > 1.5xULN
- BILI > 2xULN

(ALT or AST elevations) and BILI elevation

- (ALT > 3xULN or AST > 3xULN) and (BILI > 1.5xULN within 14 days on or after ALT or AST elevation)
- (ALT > 3xULN or AST > 3xULN) and (BILI > 2xULN within 14 days on or after ALT or AST elevation)
- (ALT > 3xULN or AST > 3xULN) and ((BILI > 2xULN and no initial ALP \geq 2xULN) within 14 days on or after AST or ALT elevation)

ALP elevations

- ALP > 1.5xULN
- ALP > 3xULN

Occurrences of AST or ALT $\geq 3 \times$ ULN together with total bilirubin $\geq 2 \times$ ULN are reported as SAE (Potential Hy's law) as described in the study protocol.

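### The on-treatment phase ends on the nominal day of Visit 13 with no allowance for visit windows, so in-window Day 253 labs can fall out of the laboratory shift tables and the ALT/AST axis of the Hy's law plot

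*SAP*

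**What the plan says.** SAP 3.1.3 (Table 4) keeps a measurement in the on-treatment phase "up to and included 28 days after the last dose of study treatment". The follow-up phase is "More than 28 days after the last dose of study treatment".

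SAP 4.2.10.8 applies that phase to two kinds of laboratory output, both for the IDMC reports and the final analysis:

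- "Shifts from baseline to maximum and minimum value during the on-treatment phase will be presented for haematology and clinical chemistry parameters".
- "Plots for the maximum on-treatment ALT/maximum on-treatment AST by maximum total bilirubin", with no phase stated for bilirubin. The same section adds that the three liver outputs take account of all measurements, unscheduled ones included.

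The elevated-liver-test table in that section is not tied to the phase; it runs from baseline to the end of the study.

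On timing, the protocol synopsis states: "Doses of MEDI6570 or placebo will be administered in the clinic SC Q4W for 32 weeks (9 doses in total"). The footnote to protocol Table 4 says: "The visit window is ± 7 days for dosing visits and ± 3 days for non-dosing visits". After an out-of-window dose, "he or she should return to the initial planned schedule for subsequent visits", so Visit 13 stays tied to Day 1 and does not move with the actual last dose. Protocol Table 5 sets Visit 13 at Day "253 (- 4 to + 11 days"). SAP Table 3 assigns laboratory values from Days 244 to 271 to the Day 253 analysis visit.

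Under the current schedule, hematology and chemistry are drawn on Days 1, 10, 29, 57, 113 and 169, before dosing on the dosing days, and then on Days 253 and 325.

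**The concern.** A phase boundary that falls on a visit's nominal day splits that visit by scheduling accident. Of two participants who both attend Visit 13 within its window, one contributes to the worst-value tables and the other does not, depending only on the gap since the last dose.

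Day 253 is an awkward visit to split. On the Amendment 2 schedule it is the only scheduled lab after doses 7, 8 and 9 that can count as on-treatment. If it is classed as follow-up, that participant's worst on-treatment value comes from samples taken no later than the pre-dose draw on Day 169. Platelet monitoring is one of the mitigations that protocol Table 6 lists for the bleeding risk. The SAP gives liver tests a table that runs to the end of the study but specifies no such table for platelets or hemoglobin.

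**Working it through.** **Inputs.** On-treatment limit: last dose + 28 days, inclusive (SAP Table 4). Nine doses every 28 days from Day 1 (SAP 3.4). Dosing window ±7 days (protocol Table 4 footnote). Visit 13 window −4 to +11 days (protocol Table 5). SAP laboratory window for Day 253: Days 244 to 271 (SAP Table 3).

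**1. Reproduce the plan's limit.** Dose 9 = 1 + 8 × 28 = Day 225. Limit = 225 + 28 = Day 253. The extended exposure in SAP 3.4.1 gives 225 − 1 + 28 = 252, which matches its top category (≥ 252). The 28 days are one dosing interval, with no margin.

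**2. Permitted days.** Dose 9: 225 ± 7 = Days 218 to 232 (15 days). Visit 13: 253 − 4 to 253 + 11 = Days 249 to 264 (16 days).

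**3. Follow-up days by day of dose 9.** For dose 9 on day D, count visit days later than D + 28.

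| Dose 9 | Last on-treatment day | Follow-up, protocol window | Follow-up, SAP window |
|---|---|---|---|
| Day 218 | 246 | 16 of 16 (100%) | 25 of 28 (89.3%) |
| Day 222 | 250 | 14 of 16 (87.5%) | 21 of 28 (75.0%) |
| Day 225 | 253 | 11 of 16 (68.75%) | 18 of 28 (64.3%) |
| Day 228 | 256 | 8 of 16 (50%) | 15 of 28 (53.6%) |
| Day 232 | 260 | 4 of 16 (25%) | 11 of 28 (39.3%) |

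For dose 9 on Days 218 to 220 the phase closes on Days 246 to 248, before the Visit 13 window opens on Day 249.

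**4. All in-window combinations.** With dose offset d from −7 to 7 and visit offset v from −4 to 11, the value is follow-up when v > d. For d = −7, −6 and −5 there are 16 such v each, 48 in total. For d = −4 to 7 there are 15, 14, …, 4, which sum to 114. Total 48 + 114 = 162 of 15 × 16 = 240, or 67.5%.

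**5. From days to labs.** Steps 3 and 4 count calendar days. The documents give no visit-timing data, so the share of labs needs an assumption:

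- Everyone exactly on schedule: 0%.
- Visit 13 centered on Day 253 (SD 1 to 5 days) and dose 9 on Day 225 (SD 1 to 4 days), normal, independent and cut off at the windows: 37% to 56%.
- The same, with Visit 13 centered mid-window (Day 256.5): 71% to 98%.
- Dose 9 and Visit 13 late by the same number of days: the gap stays at 28 and the lab stays on-treatment.

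**6. Scheduled on-treatment labs after dose 7, Amendment 2 schedule.** The Day 169 sample precedes dose 7, and Days 197 and 225 have no safety labs. That leaves one lab (Day 253) if it is drawn within 28 days of the last dose, otherwise none.

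**The case against.** A reader might infer more than the documents support, in three ways.

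- *Most Day 253 labs are lost.* The 69% and 67.5% are shares of permitted days and combinations, not of labs. A Day 253 lab after a Day 225 dose is on-treatment, and under clustered timing the share can be below half.
- *The trial has no on-treatment labs after doses 7 to 9.* That holds only for participants on the Amendment 2 schedule whose Visit 13 falls past 28 days. Participants who passed Days 197 and 225 under earlier versions had labs there, and SAP 3.1.2 still counts those visits as scheduled.
- *Late toxicity would be hidden.* By-visit summaries by group give the minimum and maximum at Day 253 whatever the phase. The listings and the elevated-liver-test table also keep these values, treatment-emergent adverse events include the follow-up phase, and potential Hy's law cases are reported as SAEs.

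The rule for the plot is also less definite than its wording suggests, because the sentence about all measurements can be read as overriding the on-treatment restriction. That ambiguity needs settling; it does nothing for the shift tables.

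The two obvious remedies have side effects. Running these outputs to the end of the study brings in Day 325 or Day 405 labs, so follow-up length would differ by protocol version. Lengthening the phase to 46 days (264 − 218) still misses the SAP window's last day after an early dose 9 (271 − 218 = 53) and a skipped dose 9 (253 − 197 = 56). It would also change adverse event phase assignment, End of Treatment values and the last on-treatment ECG.

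These points narrow the claim and the remedy. They do not remove the mismatch, and a group minimum at one visit does not replace a within-participant worst shift.

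**Conclusion.** The point holds in a limited form. The on-treatment limit coincides with nominal Visit 13 and ignores both visit windows, so the SAP as written omits some permitted Day 253 labs from the shift tables and, literally read, from the ALT/AST axis of the Hy's law plot. The exact result is 11 of 16 permitted visit days when dose 9 is on Day 225. The share of labs cannot be derived from the documents; the percentages in step 5 rest on assumed timing and show only that it could be anything from none to well over half. The practical loss is greatest for hematology, where no worst-value table to the end of the study is specified. The data stay visible elsewhere by treatment group, so this is a defect in particular summary outputs and does not mean that safety data go uncollected or unreported.

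**What to change.** In SAP 4.2.10.8, state that the laboratory shift tables and both axes of the Hy's law plot use all values after the first dose that are either in the on-treatment phase or assigned to the Day 253 analysis visit (Days 244 to 271). State that bilirubin uses the same period as ALT and AST, which also settles how the sentence about all measurements applies to the plot. Because Days 249 to 264 lie inside Days 244 to 271, every permitted Visit 13 is then included, even if dose 9 was early or missed. Leave Table 4 unchanged for adverse event phases and its other uses.

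The cost is a sentence or two in the SAP, documented before unblinding, and a small programming change; no new data are needed. The downside is that some values taken more than 28 days after the last dose enter these outputs, including Day 253 values from participants who stopped treatment early. A table footnote should say so. SAP 4.1 already includes data after treatment discontinuation by default.

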3.2 Baseline assessments and other subject-specific characteristics

3.2.1 Demographic and subject characteristics

Demographic and subject characteristics include age (years), age group (>=21-<40; >=40 - <50; >=50 -<65; >=65), sex, race, height (cm), weight (kg), body mass index (BMI) and ethnicity as well as indication [Non-ST segment elevation myocardial infarction (NSTEMI), ST segment elevation myocardial infarction (STEMI)], type of coronary procedure (Diagnostic coronary angiography only, Coronary intervention/revascularisation), extent of disease at start of angiography, procedure type [Percutaneous coronary intervention (PCI), Coronary artery bypass grafting (CABG), No procedure], stent (yes, no), type of stent, stent(s) placed for treatment of qualifying MI (yes, no) and vessels treated (left main, left anterior descending and branches, right coronary artery and branches, left circumflex artery and branches, ramus branch).

Age is the age at screening as reported in the eCRF. BMI (kg/m²) is calculated as: weight (kg)/[height (cm)/100]². Only baseline values are included in the demographic and subject characteristics.

3.2.2 Medical history

Medical history includes medical and cardiac history and risk factor. They are coded by the most up to date version of Medical Dictionary for Regulatory Activities (MedDRA).

3.3 Efficacy and safety variables

The primary objective of the study is the evaluation of the effect of MEDI6570 on non-calcified plaque volume in the most diseased coronary segment (NCPV_{MD}) compared with placebo. The effect will be evaluated by using as primary endpoint the change from baseline to Day 253 in NCPV_{MD}, as measured by CTA imaging.

Secondary and Exploratory efficacy endpoints are described in sections [3.3.2](#) and [0](#).

Additional secondary objectives are the evaluation of pharmacokinetics (PK) and immunogenicity of MEDI6570. Furthermore, the safety of MEDI6570 compared with placebo will be explored in terms of adverse events (AE) including serious adverse events (SAEs), laboratory evaluations, vital signs, and Electrocardiogram (ECG) analyses.

3.3.1 Primary efficacy endpoint

The primary efficacy endpoint is the change from baseline to Day 253 in NCPV_{MD} (mm³), as measured by CTA imaging. NCPV_{MD} is assigned to the analysis visits as described in section [3.1.2](#) and will be measured and compared to placebo.

The most diseased coronary segment is defined as the coronary segment with the highest non-calcified plaque volume on the baseline scan that also has a matching evaluable segment on Day 253 scan. Specific algorithms for programming are provided in a separate CTA imaging guidance document (Version 4.0) finalized before database lock.

3.3.2 Secondary efficacy endpoints

Secondary efficacy endpoints include:

- Change from baseline to Day 253 in NT-proBNP
- Change from baseline to Day 253 in Left ventricular function: ejection fraction (LVEF), Global longitudinal strain (GLS) as measured by Echocardiography
- Change from baseline to Day 253 in other related imaging parameters as assessed by CTA (Global non-calcified plaque volume and Low attenuation plaque volume)

3.3.2.1 NT-proBNP

Serum samples will be collected for the Heart failure (HF) biomarker NT-proBNP (pg/mL). The central laboratory result of NT-proBNP is assigned as per timepoint related to analysis visits (Table 3). Log-transformed value of NT-proBNP will be used for the analysis for comparison with placebo. Change from baseline will be defined as the log-transformation of the post-baseline visit value minus the log-transformation of the baseline value. Results will be derived for all subjects and then for a subset of subjects with reduced ejection fraction (defined as <50% at baseline).

3.3.2.2 LVEF and GLS

LVEF (%) and GLS (%) are other secondary endpoints for evaluating the effect of MEDI6570 on HF. The central laboratory result of LVEF and of GLS is assigned as per timepoint related to analysis visits (Table 3). Change from baseline to Day 253 in LVEF and in GLS by echocardiography imaging will be measured and compared with placebo. Results will be derived for all subjects and then for a subset of subjects with reduced ejection fraction (defined as <50% at baseline).

3.3.2.3 Parameters assessed by CTA

Secondary endpoints that are measured by CTA will be analysed based on CTA Analysis Population. CTA imaging results will be assigned as per timepoint related to analysis visits (Table 3). Change from baseline to Day 253 in Global non-calcified plaque volume (NCPV mm³) and in Low attenuation plaque volume (LAPV, mm³) will be measured and compared to placebo. The CTA parameters are measured at the level of the coronary segment. Prior to computing change from baseline, global values will be derived programmatically. Specific algorithms for programming are provided in a separate CTA imaging guidance document (Version 4.0) finalized before database lock.

3.3.3 Other secondary endpoints

Other secondary endpoints include:

- Immunogenicity [Anti-drug antibody(ies) (ADA) incidence and Titre]
- Pharmacokinetic concentrations

3.3.3.1 Immunogenicity parameters

Immunogenicity parameters include:

- ADA
- Titre

The Immunogenicity population will be used for the immunogenicity analyses. Descriptive statistics will be provided at baseline, Day 10, Day 29, Day 57, Day 85, Day 113, Day 122, Day 141, Day 169, Day 197, Day 225, Day 253 and Day 325/405. ADA samples may also be tested further for characterization of ADA response. ADA and Titre results will be assigned as per timepoint related to analysis visits (Table 3).

3.3.3.2 PK parameters and PK concentration

[figure not shown]
Individual serum concentrations ($\mu\text{g/mL}$) of MEDI6570 and summary of serum concentrations of MEDI6570 will be presented at baseline, Day 10, Day 29, Day 57, Day 85, Day 113, Day 122, Day 141, Day 169, Day 197, Day 225, Day 253 and Day 325/405 based on all subjects in the PK population. PK results will be assigned as per timepoint related to analysis visits (Table 3).

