Randomization to the CCI dose group was removed.	
• To reduce the overall sample size of the study• The current number of participants in the [REDACTED] mg dose group is expected to provide sufficient dose-response information on the PK-PD relationship and endpoints, and is unlikely to be the dose with the optimal clinical risk-benefit balance.	Section 1.1 Synopsis; Section 1.2 Schema; Section 4.1 Overall Design; Section 4.3 Justification for Dose; Section 6.1 Study Interventions Administered, Table 8 Investigational Products; Section 6.2.3 Dose Preparation Steps, Table 9 Dose Preparation for Fixed SC Doses of CCI [REDACTED] and CCI [REDACTED] mg MEDI6570 and Placebo; Section 6.3.1 Randomization Procedure; Section 6.3.2 Blinding Procedure; Section 6.3.3 Unblinding for Interim Analysis Purposes (section deleted); Section 9.2 Sample Size Determination; Section 9.5 Interim Analyses

Table 1 Substantial Changes to the Protocol

Description of Change	Brief Rationale	Sections Affected
The number of participants was reduced from 792 to 400. CC1 	To reduce the overall sample size and improve feasibility of completion while maintaining acceptable power to inform development program decisions	Section 1.1 Synopsis; Section 1.2 Schema; Section 4.1 Overall Design; Section 9.2 Sample Size Determination
The 2 formal interim analyses were removed.	The interim analyses were administrative in nature. The full study results will be used for decision making on future development options. The study was designed to continue to completion regardless of the results of the interim analyses.	Section 1.1 Synopsis; Section 1.2 Schema; Section 4.1 Overall Design; Section 6.3.3 Unblinding for Interim Analysis Purposes (section deleted); Section 9.4.1 General Considerations; Section 9.5 Interim Analyses
The Day 405 visit (formerly Visit 16) was removed and the Day 325 visit (Visit 14) (formerly Day 334 [Visit 15]) is the new End of Study Visit	The safety follow-up visit will be performed approximately 3 months after the last dose (shortened from 6 months). CC1 	Section 1.1 Synopsis; Section 1.3 Schedules of Activities, Table 5 Schedule of Activities: Follow-up Period; Section 4.1 Overall Design

Table 1 Substantial Changes to the Protocol

Description of Change	Brief Rationale	Sections Affected

 • CCI [REDACTED] • [REDACTED] • [REDACTED] • [REDACTED] 		

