For days on or after the first dose of study treatment: date of assessment - date of first dose of study treatment + 1.

For days before the first dose of study treatment: date of assessment - date of first dose of study treatment.

For the purpose of the statistical analysis, efficacy and safety variables are allocated to the analysis visit as reported in the table below. Analysis visit is defined based on analysis day the visit occurred, visit window reported below, and using scheduled or unscheduled eCRF visits. The allocation to analysis visit windows is performed after the imputation of date of first and last doses of IP as in Section 3.1.1. Measurements with missing or partially missing dates cannot be imputed to any analysis visit.

Table 3 Scheduled analysis visit windows

Analysis visit	CSP visit name		Visit window (days)	
	After amendment 2 ^d	Before amendment 2	CTA – ECHO – Biomarkers ^a	Other parameters
Pre-treatment	Visit 2 – Visit 3		<= 1 ^b	
Day 10	Visit 4		CCI : 3 -17	3 -17
Day 29	Visit 5		Biomarkers: 21 – 37	21 – 37
Day 57	Visit 6		CCI : 49 – 65	49 – 65
Day 85	Visit 7		Biomarkers: 77 – 93	77 – 93
Day 113	Visit 8		Biomarkers: 105 – 121	105 – 121 ^c
Day 122	Visit 9		CTA: 114 – 140 CCI and biomarkers: 118-126	118 – 126
Day 141	Visit 9	Visit 10	CCI : 133 - 149	133 - 149
Day 169	Visit 10	Visit 11	CCI : 161 - 177	161 - 177
Day 197	Visit 11	Visit 12		188 - 206
Day 225	Visit 12	Visit 13	Biomarkers: 217 - 233	217 - 233
Day 253	Visit 13	Visit 14	CCI : 249-264 Biomarkers except CCI : 249 - 285 CTA, ECHO: 234 - 326	244 - 271
Day 325/405	Visit 14	Visit 16	CCI : 317 - 333/ 394 - 416	317 - 333/ 394 - 416

^a CCI , NT-proBNP, CCI CCI NT-proBNP, we will include analysis visits of pre-treatment, Day 113 and Day 253. CCI we will include analysis visits of pre-treatment, Day 10, Day 29, Day 57, Day 113, and Day 253.

^b Includes all measurements collected before or on day 1 prior to first dose of IP. If measurement is done on day 1 but time of collection is missing and per CSP parameter should be collected before first dose of study, analysis phase is “Pre-treatment”.

^c to avoid conflict between analysis visit Day 113 and Day 122, for participants who performed visit 8 before amendment 2 the visit window will be 109 – 117. For participants with missing date of reconsent for amendment 2 or who did Visit 8 before 25Jan2022 (Date of migration in EDC) the visit window will be also 109 – 117.

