^d Some scheduled visits were removed after the protocol amendment 2 but these analysis visits will be included in the analysis because they fall in the analysis windows defined before the protocol amendment 2. Please check the latest version of the protocol for more details.

End of Treatment is defined as the last value in the on-treatment phase as defined in section 3.1.3.

Baseline visit window will be derived for the analysis purpose and includes measurements collected prior day 1 or at day 1 prior to the first dose of study treatment.

An analysis visit is classified as scheduled if it was requested per the Schedule of Activity at the time the patient did the visit (especially if visit done before or after protocol amendment 2). Except otherwise specified, the data being assigned as unscheduled analysis visits will not be summarized in tables or presented in figures but only displayed in listings.

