ADA will be summarized by visit at final analysis only as categorical variable with the number and percentages with a positive result at the baseline, Days 10 to 141, Day 225, Day 253 and Day 325/405. Immunogenicity titre will be summarized descriptively as continuous variable, only for ADA positive tests, with median, interquartile range, minimum and maximum, at same analysis visits as ADA.

ADA positive subjects will also be listed at final analysis only.

All ADA analyses above except the summary statistics by visit will include scheduled and unscheduled ADA measurements.

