4.2.9.2 PK analysis

Tables and figures will be based on the PK population and presented for each treatment group at final analysis.

Individual serum concentrations ($\mu\text{g/mL}$) of MEDI6570 will be summarized descriptively as a continuous variable by analysis visit for each treatment group and tabulated. Descriptive statistics include, but not limited to, geometric mean (GeoMean), geometric coefficient of variation (GeoCV), arithmetic mean, SD, geometric SD (GeoSD), minimum, median, maximum, n and n below the lower limit of quantification (LLOQ). The LLOQ for MEDI6570 is 0.03280 $\mu\text{g/mL}$.

GeoMean and GeoSD of serum concentrations ($\mu\text{g/mL}$) of MEDI6570 vs analysis visit and treatment group will be presented in graph using log-linear and linear scale.

Individual serum concentrations ($\mu\text{g}/\text{mL}$) of MEDI6570 vs actual time will be plotted by treatment group using log-linear and linear scale.

Individual serum concentrations ($\mu\text{g}/\text{mL}$) of MEDI6570 for each actual time point will be listed.

If data allows, impact of ADA on PK will be evaluated by plotting serum concentrations ($\mu\text{g}/\text{mL}$) time profile of MEDI6570 by ADA category using box plot and by plotting individual serum concentrations ($\mu\text{g}/\text{mL}$) time profile of MEDI6570 by ADA category using spaghetti plot.

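### The SAP assigns the Day 325 and the earlier Day 405 end-of-study visits to one analysis visit, so descriptive follow-up summaries pool values nominally 100 and 180 days after the last dose

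*SAP*

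**What the plan says.** SAP section 3.1.2 allocates efficacy and safety variables to analysis visits by study day, using Table 3. The last row of that table is Day 325/405. It corresponds to Visit 14 after Amendment 2 and to Visit 16 before it, and its window for PK, ADA, laboratory and vital-sign data reads "317 - 333/ 394 - 416".

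The reporting sections carry the joint label forward:

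- Section 3.3.3.2 lists concentrations at "Day 225, Day 253 and Day 325/405 based on all subjects in the PK population", and section 4.2.9.2 says they "will be summarized descriptively as a continuous variable by analysis visit for each treatment group and tabulated". Geometric means are also plotted against analysis visit.
- Section 3.3.3.1 lists the same joint time point for ADA and titre. Section 4.2.9.1 asks for the "number and percentages with a positive result at the baseline, Days 10 to 141, Day 225, Day 253 and Day 325/405", with titre summarized at the same visits.
- Sections 4.2.10.8 and 4.2.10.9 summarize laboratory values and vital signs at each visit.

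The two days arise because Amendment 2 removed the Day 405 visit and made Day 325 the end of study. The protocol's table of substantial changes says: "The safety follow-up visit will be performed approximately 3 months after the last dose (shortened from 6 months"). The same entry shows that Day 325 replaced a Day 334 visit, the former Visit 15.

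**The concern.** A by-visit row should describe patients at about the same time. This one does not: its two windows do not overlap, and both lie in washout, when drug concentration is falling and ADA status may be changing. A geometric mean or a percentage positive for the joint row describes neither Day 325 nor Day 405.

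The mixture also need not be the same in every arm. Under Amendment 2 nobody new is randomized to the legacy dose (protocol section 6.1, footnote to Table 8), while the two continuing doses and placebo kept recruiting. Comparing arms on this row could then partly compare time since last dose.

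PK and immunogenicity during follow-up are named secondary objectives, and this is the only Table 3 row after Day 253.

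**Working it through.** The plan states no figure to reproduce here. The check is of timing, of the possible mix by arm, and of what can be said about size.

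**Timing.** The last scheduled dose is on Day 225 (SAP section 3.4).

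- Amendment 2 visit: 325 − 225 = 100 days; window 317 − 225 = 92 to 333 − 225 = 108 days.
- Earlier visit: 405 − 225 = 180 days; window 394 − 225 = 169 to 416 − 225 = 191 days.
- Gap: 405 − 325 = 80 days nominally, and between 394 − 333 = 61 and 416 − 317 = 99 days across the windows.

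**Who can contribute a Day 405 value.** SAP Table 3, footnote c, gives 25 January 2022 as the data-capture migration date for Amendment 2. Day 405 is 404 days after Day 1, so reaching it by then needs a first dose by 17 December 2020. That is before Amendment 1 (10 March 2021), so these are Version 1.0 participants. Migration is not a hard cut-off, but the dates suggest that few people reached Day 405.

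**Mix by arm.** The protocol's amendment history gives Version 1.0 allocation as 1:1:1:1. The protocol plans 111 evaluable participants in each continuing dose group and 27 in the legacy group. If equal numbers per arm reached Day 405 (an assumption), the share would be 111/27 = 4.1 times larger in the legacy group.

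**Illustration of size, on assumptions only.** The readable text gives no half-life. Assume first-order decline with a half-life h of 14, 21 or 28 days.

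- Ratio of the Day 325 to the Day 405 concentration = 2^(80/h) = 52.5, 14.0 or 7.2.
- With a fraction f of Day 405 values, pooled geometric mean ÷ Day 325 geometric mean = 2^(−80f/h).
- Suppose, hypothetically, that 5 participants per arm contribute Day 405 values. With f = 5/111 = 0.045 the ratio is 0.84, 0.89 or 0.91. With f = 5/27 = 0.185 it is 0.48, 0.61 or 0.69.

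These are not estimates. They also ignore SAP section 4.2.9.2.1. There, values below the quantification limit are set to that limit when they make up at most half of a time point; above half, the geometric mean is not calculated. On the assumed half-lives Day 405 is 180/28 = 6.4 to 180/14 = 12.9 half-lives after the last dose, so those rules may well apply. They could cap the shift, or leave the pooled row with no geometric mean.

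**The former Day 334 visit.** Table 3 has no row for Visit 15. Day 334 is one day beyond the 317 to 333 window, so an on-schedule value has no analysis visit, while one taken a day or more early could enter the joint row. The same participant's Day 405 value could then enter it too. The rule in section 3.1.2 for several values in one window opens with CTA, and whether it reaches other data is unclear.

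**The case against.** **No sentence says the two days are pooled.** True: the slash could be shorthand for two displays. But Table 3 makes it one analysis visit, and the reporting sections summarize by analysis visit. No readable rule separates the two days, whereas Day 122, also dropped by Amendment 2, keeps its own row. Pooling is what the plan produces as written.

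**The outputs that matter do not use this row.** This largely stands. ADA incidence is defined per participant over all assessments. Individual concentrations are plotted and listed by actual time. Adverse events are tabulated by phase, and ECG findings are only listed. No hypothesis test uses the row. A reader might infer that the secondary PK and immunogenicity objectives are compromised; the documents do not support that.

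**The size is unknown and may be small.** This stands. A reader might infer a many-fold bias, or that the legacy dose will appear to clear faster. Neither follows without the half-life, the Day 405 counts and the effect of the quantification-limit rules.

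**The Day 334 point rests on a schedule not in the documents.** This stands in part. The earlier schedule of activities is absent, so the visit's window and sampling are unknown, and it cannot be said that data are lost. What can be said is that Table 3 has no row for that visit.

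**Splitting the row does not fix time since last dose exactly.** Also true. Visits are counted from the first dose, and participants who stop treatment early stay in by-visit summaries. The split removes the scheduled 80-day mixture, not that residual variation.

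**Conclusion.** The point holds for descriptive by-visit reporting. As written, the last row of the PK, ADA, titre, laboratory and vital-sign summaries, and the last point of the geometric-mean concentration plot, pool values nominally 100 and 180 days after a Day 225 last dose. The Day 405 share may be larger in the legacy dose group. That rests on when the group was randomized, not on any count in the documents.

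The distortion cannot be quantified from the documents. The primary analysis and the outputs named above as independent of this row are untouched. The change is worth making because it is nearly free and the affected row is the only by-visit summary of late follow-up.

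**What to change.** In SAP Table 3, replace the joint row with two analysis visits: Day 325 (Days 317 to 333) and Day 405 (Days 394 to 416). Carry both, each with its own n, through sections 3.3.3.1, 3.3.3.2, 4.2.9.1 and 4.2.9.2, the geometric-mean plot, and the laboratory and vital-sign tables, and do not pool them. Apply the quantification-limit rules to each visit separately.

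State where values from the former Visit 15 (Day 334) are assigned, using the window that visit had in the earlier protocol version.

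The cost is SAP and table-shell wording and one extra row per by-visit table. The Day 405 row will have small n. No new data are needed.
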